- *Reduced neurological disability at hospital discharge (Aim 2)*
- *Reduced neuropsychological and functional deficits among survivors at 180 days (Aim 3)*

D.1.2. Overview

Design: Prospective protocol implementation study with an observational comparison group [REOX II (intervention component) versus REOX I (observational component)]

Participants: Adult patients resuscitated from cardiac arrest

Enrollment location: Emergency Departments of 6 urban academic medical centers

Intervention: Implementation of a clinical protocol for rapid FiO₂ optimization after ROSC from cardiac arrest.

Primary outcome: Good neurological outcome (defined as Modified Rankin Scale ≤ 3 ⁴⁵ at hospital discharge).

Secondary outcomes: Neuropsychological tests and ability to return to work among survivors at 180 days.

Mechanistic outcomes: Oxidative stress markers (IsoPs/IsoFs) in plasma 0-6 hours after ROSC.

Estimated sample size and study duration: 280 patients (205 from REOX I and 75 from REOX II).

[figure not shown]
D.2. REOX II Study Protocol

Study setting and population: This study is the second phase in a two-phase study. The initial phase, REOX I, was an observational-only study. As in REOX I, REOX II will identify subjects with return of spontaneous circulation (ROSC) after cardiac arrest in 6 hospitals (Cooper University Hospital, Camden, NJ; Hospital of the University of Pennsylvania and Penn-Presbyterian Medical Center, both in Philadelphia, PA; University of Mississippi Medical Center, Jackson, MS; Methodist Hospital, Indianapolis, IN; and Beth Israel Deaconess Medical Center, Boston, MA). The inclusion criteria are: age > 17 years; cardiac arrest; ROSC achieved; comatose (Glasgow Coma Scale motor score < 6) after ROSC; and clinician intent to treat with target temperature management. The exclusion criteria are: presumed etiology of arrest is trauma, hemorrhage or sepsis; resident of a nursing home or other long-term care facility; known or clinically apparent pregnancy; known lack of commitment to aggressive support by next of kin; and any other condition, that, in the opinion of the investigator, would preclude the subject from being a suitable candidate (e.g. end stage chronic illness with no reasonable expectation of survival to hospital discharge).

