Standard care elements
24/7 capability for interventional cardiac catheterization (if needed)
Standardized patient selection for TH (i.e. GCS motor <6 after ROSC)
Target temperature goal for TH of 32-36°C
Maintain TH target temperature 24 hours
Controlled rewarming to avoid hyperpyrexia after TH completion
24/7 capability for goal-directed hemodynamic support interventions
24/7 capability for continuous electroencephalographic monitoring
Evidence-based approach to neurological prognostication (e.g. wait ≥72 hours after ROSC before support limitations for poor neurological prognosis)

Instead these patients will have clinician-directed FiO_2 titration after ROSC. Data will be prospectively collected on these patients (see “*Data Collection*” below) and we will approach subjects or surrogates at a later time for written informed consent and HIPAA authorization for participation in the observational component of the study.

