Outcome measures: The primary outcome will be neurological disability at hospital discharge assessed with the Modified Rankin Scale (mRS),^{48,49} a well-validated and widely used outcome measures in stroke clinical trials. The scale runs from 0-6, from perfect health without symptoms to death (**Table 4**). All raters will be trained and certified in mRS assessment⁵⁰ and will use a structured questionnaire and interview, which have been shown to produce very good interobserver reliability.^{51,52} We will measure the Full Outline of UnResponsiveness (FOUR) Score^{53,54} at 72 hours post-ROSC (**Table 5**). The FOUR Score consists of four components with a maximum score of four for each component and allows for assessing intubated patients and brainstem reflexes. We will also perform neuropsychological testing at 180 days after resuscitation for all patients who survived to hospital discharge. We will use an NHLBI-sponsored methodology for performing centralized, telephone-based cognitive testing, which has been previously validated for use in multi-center clinical studies.⁵⁵⁻⁶⁰

Neuropsychological testing will use validated instruments across five cognitive domains: (1) attention, Wechsler Adult Intelligence Scale-IV-digit span; (2) reasoning, Wechsler Adult Intelligence Scale-IV-similarities; (3) immediate and delayed memory, Wechsler Memory Scale-III-logical memory I and II; (4) verbal fluency, Controlled Oral Word Association Test; and (5) executive functioning, Hayling Sentence Completion Test. We will also assess

Table 4: Modified Rankin Scale

Scale	Description
0	No symptoms.
1	No significant disability. Able to carry out all usual activities, despite some symptoms.
2	Slight disability. Able to look after own affairs unassisted, but unable to carry out all previous activities.
3	Moderate disability. Requires some help, but able to walk unassisted.
4	Moderately severe disability. Unable to walk and attend to own bodily needs unassisted.
5	Severe disability. Requires constant nursing care and attention, bedridden, incontinent.

Table 5: Full Outline of UnResponsiveness Score

Component	Scoring
Eye Response	4 = eyelids open or opened, tracking, or blinking to command 3 = eyelids open but not tracking 2 = eyelids closed but open to loud voice 1 = eyelids closed but open to pain 0 = eyelids remain closed with pain

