$$\text{TWA-SaO}_2 = [(SaO_{2a} * \text{Time a}) + (SaO_{2b} * \text{Time b}) + \dots (SaO_{2z} * \text{Time z})] / (\text{Time a} + \text{Time b} + \dots \text{Time z})$$

We will build a multivariable regression model to test the association between TWA-PaO₂ and mRS at hospital discharge, adjusting for covariates previously demonstrated to be associated with poor neurological outcome after cardiac arrest. Covariates to be considered include: (1) pre-arrest comorbidities (Charlson index⁶⁹), (2) prolonged downtime (downtime > 20 minutes) (yes/no), (3) initial arrest rhythm (pulseless electrical activity/asystole vs. ventricular tachycardia/ventricular fibrillation), and (4) arrest location (in-hospital vs. out-of-hospital).⁷⁰⁻⁷⁵ In addition, in order to account for patients with lung injury (i.e. inability to maintain adequate oxygenation) we will add PaO₂/FiO₂ < 100mmHg (yes/no) to the regression model. We will build separate models to test the association between TWA-PaO₂ (adjusting for the five covariates above) and each of the five cognitive domains in our neuropsychological testing. We will then repeat these analyses using TWA-SaO₂ as the exposure variable of interest. This approach will not only allow us to test for an independent association between the exposure and neurological disability and neuropsychological deficits, but will also allow us to pinpoint one or more types of cognitive deficit (e.g. attention, executive function) most closely associated with the exposure. Given outcome measures that are quantitative (i.e. z-score for each cognitive domain) or semi-quantitative (i.e. mRS at hospital discharge), we will treat these outcomes as *continuous* dependent variables for modeling. Using continuous measures of the exposure and outcomes (rather than collapsing the data into categorical variables) will permit detection of subtle effects that could be missed if only categorical analyses were employed.

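### The adjusted mRS and cognitive models contain no direct measure of neurological injury after ROSC, although the GCS motor score must be assessed for eligibility

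*Combined protocol and SAP*

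**What the plan says.** The multivariable model in the Analysis section of D.2 relates time-weighted average PaO2 over the first 24 hours to mRS at discharge, "adjusting for covariates previously demonstrated to be associated with poor neurological outcome after cardiac arrest". The list begins "Covariates to be considered include: (1) pre-arrest comorbidities (Charlson index⁶⁹), (2) prolonged downtime (downtime > 20 minutes) (yes/no", continues with initial rhythm, and ends its numbered items with "and (4) arrest location (in-hospital vs. out-of-hospital". For lung injury the plan then says "we will add PaO₂/FiO₂ < 100mmHg (yes/no) to the regression model". The cognitive-domain models are fitted "adjusting for the five covariates above", and the whole set is repeated with SaO2 as the exposure. The stated purpose is to test for an independent association in a design that is not randomised.

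Neurological status after ROSC appears in three other places:

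- **Study setting and population:** the inclusion criterion "comatose (Glasgow Coma Scale motor score < 6) after ROSC".
- **Table 3 (standard care elements):** "Standardized patient selection for TH (i.e. GCS motor <6 after ROSC".
- **Outcome measures:** the FOUR score, taken "at 72 hours post-ROSC".

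The SOFA score is computed without its neurological component. The Data collection paragraph does not name the GCS.

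**The concern.** The outcomes are neurological, so a patient's neurological state soon after ROSC is an obvious candidate predictor. The plan uses the motor score only as a yes/no gate. Any difference in prognosis between a motor score of 1 and one of 5 is left to the proxies in the model or to the error term.

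Two things are at stake. The first is precision: leaving out a baseline predictor of outcome widens the confidence interval for the oxygen effect. The second is bias. About 205 of the 280 patients come from REOX I, where clinicians chose the FiO2. If they kept more deeply comatose patients on more oxygen, the PaO2 slope would look harmful without any oxygen effect. If the link ran the other way, a real harm could be hidden.

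The plan's own background (A.3) describes a replication in which the link between hyperoxia and mortality disappeared after further adjustment. This study is meant to settle that uncertainty, and a result without baseline neurological severity would be open to the same challenge.

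**Working it through.** **1. Is the covariate set closed?** The phrase introducing the list is open in tone. However, the cognitive models refer back to five covariates, and the Sample Size section counts six independent variables, which is the exposure plus five. The set is therefore closed, and no item in it measures neurological status after ROSC. FOUR at 72 hours cannot fill the gap because it follows the 24-hour exposure window.

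**2. The plan's own figure.** Inputs from Sample Size: R² = 0.15, six predictors, 80% power, alpha 0.05.
- f² = 0.15/0.85 = 0.1765. The omnibus F test has noncentrality N·f² on (6, N−7) degrees of freedom.
- Smallest N = 84. Power at N = 85 is 0.808, so the plan's 85 reproduces.
- 85 × 1.15 = 97.75, rounded to 98, and 98/0.35 = 280. Both follow.

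**3. Precision.** The documents give no correlation between motor score and outcome, so this is an assumed range. Let ρ be the partial correlation of motor score with outcome given the five covariates, with PaO2 unrelated to coma depth. Adding the score cuts residual variance by ρ², so the f² for the PaO2 coefficient becomes f²/(1−ρ²). The test is a 1-df noncentral F. The f² that gives 80% power with six predictors is 0.0282 at N = 280 and 0.0947 at N = 85.

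| ρ | Variance removed | Power with motor score added |
|---|---|---|
| 0.2 | 4% | 81.6% |
| 0.3 | 9% | 83.6% |
| 0.4 | 16% | 86.4% |
| 0.5 | 25% | 89.9% |

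The results are the same at N = 280 and N = 85 to the decimal shown.

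**4. Confounding.** This is also on assumed inputs. Let c be the partial correlation of deeper coma with PaO2, and let oxygen have no effect. The model without motor score then sees an induced correlation r = c·ρ, and rejects with the power of a 1-df test at f² = r²/(1−r²). For example, c = 0.2 and ρ = 0.3 give r = 0.06.

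| c | N = 280 (mRS), ρ = 0.3 / 0.4 / 0.5 | N = 85 (cognitive), ρ = 0.3 / 0.4 / 0.5 |
|---|---|---|
| 0.05 | 5.7% / 6.3% / 7.0% | 5.2% / 5.4% / 5.6% |
| 0.1 | 7.9% / 10.2% / 13.3% | 5.9% / 6.5% / 7.4% |
| 0.2 | 17.1% / 26.8% / 38.8% | 8.5% / 11.3% / 15.0% |

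At c = 0 the rate is the nominal 5%, and only the precision in step 3 is lost.

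**5. Cost of the extra term.** In the plan's omnibus formula with R² held at 0.15, a seventh predictor lowers power at N = 85 from 0.808 to 0.778. That formula gives the new variable no explanatory value. If it raised R² to 0.18 (assumed), power would be 0.87. For the PaO2 coefficient the lost degree of freedom is negligible: at N = 85, 80.0% stays at 80.0% to one decimal even if the score explains nothing.

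**The case against.** **The graded score may not exist.** Eligibility needs only the threshold. A reader might infer that a 1–5 value is on file for everyone, but no section says that it is recorded, and about 200 REOX I patients were already enrolled when the plan was written. This stands, and it makes the fix conditional on retrieval.

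**The score's timing is loose.** It is taken after ROSC at no stated time, possibly after some oxygen, sedation or paralysis. This also stands. Adjustment would be partial, and the power gains in the working are upper values for a given ρ.

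**Confounding is not shown.** A reader might infer that the oxygen estimate is confounded. The documents do not support that, because nothing in them links coma depth to FiO2 choice. In REOX II (75 planned patients) FiO2 follows a protocol aimed at a PaO2 of 60–99 mmHg, and no part of the available text gives coma depth a role in it. That should weaken a pooled correlation. The small-c rows are as admissible as the c = 0.2 row.

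**The larger ρ values are generous for the cognitive models.** There the plan expects six predictors together to explain 15% of variance, and only tested survivors contribute. At ρ = 0.2 the gain is under 2 points. This is a fair limit on size.

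**Part of the injury is already captured.** Restriction to motor score below 6, downtime, rhythm and location all carry information on the insult. It would be wrong to read the models as having no adjustment for severity. What is missing is the residual part.

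**Conclusion.** The omission is real, and no other section repairs it. It is a cheap improvement, not a flaw that invalidates the analysis.

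The precision gain depends only on motor score predicting outcome beyond the five covariates. It is about 2 to 10 points of power from a base of 80% for ρ from 0.2 to 0.5. The bias depends in addition on an undocumented link between coma depth and PaO2. False rejection in the mRS model runs from near nominal (6–7%) at c = 0.05 to 17–39% at c = 0.2. The upper range should not be carried over to the cognitive models, where c = 0.2 gives 8.5–15%. The supportable claim is that omission can confound, not that it does.

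Nor is this a sample-size error: 85, 98 and 280 all follow from the plan's inputs and steps.

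**What to change.** - Prespecify the first post-ROSC GCS motor score (1–5, as an ordered score) as a covariate in the mRS and cognitive models, for both the PaO2 and SaO2 exposures.
- Record the exact value in REOX II, with its time and whether the patient was sedated or paralysed.
- Confirm that the value can be retrieved from the medical record for REOX I patients, and state the method for missing values before the analysis is run.
- Add a sensitivity analysis that excludes scores taken under sedation or paralysis.
- State that the 72-hour FOUR score will not be used as a covariate, because it follows the exposure.

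The cost is analysis wording, chart retrieval for REOX I and one model degree of freedom. Adjustment will be partial because of sedation and the unstated timing of the score. If the graded score cannot be recovered for most REOX I patients, the plan should say so and list the lack of baseline neurological adjustment as a limitation of the independent-association claim. No patient's care changes.

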These data from animal models support the hypothesis that hyperoxia after ROSC may worsen outcomes in post-resuscitation patients. However, clinical data are few. Three preliminary retrospective multi-center analyses have been published. Two of these were published by our research team.^{24,25} In a large (n=6326) cohort of patients admitted to one of 120 U.S. ICUs after cardiac arrest, we found that post-ROSC hyperoxia was **common, an independent predictor of in-hospital death, and associated with lower functional independence among survivors.**²⁴ In a secondary analysis using the same ICU database, we found that a linear, **“dose-dependent” relationship exists between supranormal PaO₂ after ROSC and mortality**²⁵ (see *Preliminary Studies* in sections C.3.1 and C.3.2). However, a recent study from the Australian and New Zealand Intensive Care Society (ANZICS) investigators reported somewhat different results.²⁶ Using a retrospective methodology that replicated our initial study, they found that among 12,000 patients admitted to an ICU after cardiac arrest, patients with hyperoxia (defined by our previous methodology as a PaO₂ >300 mmHg) had significantly higher mortality (59% [95%CI 56-61%]) than patients with normoxia (47% [95% CI 45-50%]), but not patients with hypoxia (60% [95% CI 59-61%]). In a multivariable model adjusting for illness severity, hyperoxia had an odds ratio for mortality of 1.2 (95% CI 1.1-1.6). However, when statistical models with a number of additional adjustments were applied, the association with increased mortality was lost. They concluded that hyperoxia has no consistently reproducible independent association with mortality.²⁶ Therefore, **whether hyperoxia is associated with poor outcome in post-resuscitation patients remains unclear.** Given that post-ROSC hyperoxia exposure is extremely common²⁵, this unanswered question represents a **critical knowledge gap** for resuscitation science. Accordingly, this project will generate **new, critically important knowledge about a fundamental element of post-cardiac arrest care.**

[figure not shown]
B. INNOVATION

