Using Project IMPACT, a database of ICU admissions from 120 U.S. hospitals, we tested the hypothesis that exposure to hyperoxia (defined as a PaO₂ \geq 300 mmHg on the first arterial blood gas recorded in the ICU) was associated with increased in-hospital death among 6326 patients admitted to an ICU after cardiac arrest. We found that the patients with hyperoxia had significantly higher in-hospital mortality (63% [95% CI 60%-66%]) compared to patients with normoxia (45% [95% CI 43%-48%]; proportion difference 18% [95% CI 14%-22%]), and also compared to patients with hypoxia (57% [95% CI 56%-59%]; proportion difference, 6% [95% CI, 3%-9%]). Survival over time appears in **Figure 4**. In a model controlling for potential confounders (e.g., age, preadmission functional status, comorbid conditions, vital signs, and other physiological indices) including sensitivity analyses that adjusted for hospital factors and propensity of hyperoxia exposure, hyperoxia had an odds ratio for death of 1.8 (95% CI, 1.5-2.2).

Among survivors, hyperoxia was associated with a lower proportion of functional independence at discharge compared to patients with normoxia (29% vs. 38%, respectively; proportion difference, 9% [95% CI, 3%-15%]).

Figure 4: In-hospital death between hyperoxia and normoxia groups.

C.3.2. Dose-dependent relationship between supranormal PaO₂ and risk of death after cardiac arrest.

Kilgannon JH, Jones AE, Parrillo JE, Dellinger RP, Milcarek B, Hunter K, Shapiro NI, Trzeciak S.

[figure not shown]
Relationship between supranormal oxygen tension and outcome after resuscitation from cardiac arrest.

Circulation 2011; 123(23):2717-22.

Using the same ICU database, we tested the hypothesis that a linear, dose-dependent relationship exists between post-resuscitation supranormal oxygen tension (highest PaO₂ over the first 24 hours in the ICU) and in-hospital mortality. Among 4459 patients, the median PaO₂ was 231 (IQR 149-349) mmHg. Over ascending ranges of oxygen tension, we found significant linear trends of increasing in-hospital mortality and decreasing survival as functionally independent, $p < 0.0001$ (**Figure 5**). On multivariable analysis, a 100 mmHg increase in PaO₂ was associated with a 24% increase in mortality risk (odds ratio 1.24 [95% CI 1.18-1.31]) (**Figure 6**).

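### The TWA-PaO2 models do not name age or site and cut downtime at 20 minutes, which leaves confounding that data already collected could reduce

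*Combined protocol and SAP*

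**What the plan says.** The main analysis is in the Analysis part of D.2: "We will build a multivariable regression model to test the association between" TWA-PaO2 and mRS at discharge, "adjusting for covariates previously demonstrated to be associated with poor neurological outcome after cardiac arrest". The list opens with "Covariates to be considered include: (1) pre-arrest comorbidities (Charlson index") and continues with "prolonged downtime (downtime > 20 minutes) (yes/no"), initial rhythm (two classes) and arrest location (in or out of hospital). A PaO2/FiO2 <100 mmHg indicator is then added "in order to account for patients with lung injury". No measurement time is given for it.

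Separate models for the cognitive domains follow, "adjusting for the five covariates above". The Sample Size paragraph sizes those cognitive models on six independent variables, that is, the exposure plus five covariates.

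Other parts of the document bear on the choice:

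- Data collection (D.2) lists demographics and length of downtime, all blood gases over 36 hours and every FiO2 change.
- D.1.2 and D.2 give six hospitals. Therapeutic interventions (D.2) says that REOX I oxygen titration was left to clinicians.
- C.3.1 describes the team's earlier hyperoxia model: "In a model controlling for potential confounders (e.g., age, preadmission functional status, comorbid conditions, vital signs, and other physiological indices"), with hospital factors handled in sensitivity analyses.
- A.3 reports that in another cohort, "when statistical models with a number of additional adjustments were applied, the association with increased mortality was lost".

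**The concern.** Nobody is randomised to a PaO2. In REOX I the exposure came from clinicians' decisions at six hospitals without a titration protocol, so it may differ by hospital and by type of patient. The model is meant to show an independent association, and covariate adjustment is its main protection against confounding.

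Age is a natural candidate for any model of neurological outcome, and the team used it before. Site can influence both oxygen practice and outcome. If either is related to exposure and outcome beyond the five named covariates, the TWA-PaO2 coefficient absorbs part of that relation. Downtime is named, but a yes/no split treats 21 and 60 minutes alike and adjusts only in part. The variables needed are already in hand.

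**Working it through.** **1. What is fixed and what is open.** The count of five is attached to the cognitive models, and so is the count of six in the sizing. For the mRS model four covariates are only to be considered, and the PaO2/FiO2 flag is to be added. Neither place names age or site.

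**2. The plan's own sizing figure.** The inputs, from Sample Size, are R² = 0.15, six predictors, 80% power and alpha 0.05. For the overall F test:

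- f² = 0.15/0.85 = 0.1765
- noncentrality at n = 85: 0.1765 × 85 = 15.0
- degrees of freedom: 6 and 85 − 7 = 78
- power at 85: 80.8%; the smallest n reaching 80% is 84

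The stated 85 is reproduced. The next steps also match: 85 × 1.15 = 97.75, rounded up to 98, and 98/0.35 = 280.

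**3. One omitted confounder at n = 280.** Let r be its correlation with exposure and g its correlation with outcome, with no true exposure effect. The spurious standardised slope is r·g. The test statistic is shifted by δ = r·g·√280 = 16.73·r·g, and the rejection rate is P(Z > 1.96 − δ) + P(Z < −1.96 − δ). The values of r and g are assumptions, because the documents give none.

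| r / g | r·g | δ | False-positive rate |
|---|---|---|---|
| 0.1 / 0.1 | 0.01 | 0.17 | 5.3% |
| 0.1 / 0.3 | 0.03 | 0.50 | 7.9% |
| 0.2 / 0.2 | 0.04 | 0.67 | 10.3% |
| 0.2 / 0.3 | 0.06 | 1.00 | 17.1% |
| 0.3 / 0.3 | 0.09 | 1.51 | 32.5% |
| 0.3 / 0.4 | 0.12 | 2.01 | 51.9% |

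Simulation agrees (51–52% in the last row). In simulation over the same range, a confounder entered as a median split gives about 5–12%, and one entered as a continuous linear term gives about 5%.

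**4. The 20-minute cut.** Assume log-normal downtime with log SD 0.6 and median 15 to 30 minutes. With c = ln(20/median)/0.6 and p the share above 20 minutes, the fraction of log-downtime variance that the indicator captures is φ(c)²/[p(1 − p)].

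- Median 15: c = 0.48, p = 0.316, fraction 0.585
- Median 20: c = 0, p = 0.5, fraction 0.159/0.25 = 0.637
- Median 30: c = −0.68, p = 0.750, fraction 0.538

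So the cut keeps about 54–64% and leaves about 36–46% unadjusted.

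**5. The PaO2/FiO2 flag.** TWA-PaO2 covers the first 24 hours after ROSC, so a 0-hour PaO2 normally contributes to the exposure. Where FiO2 is near 1.0, PaO2/FiO2 is numerically close to PaO2. A continuous 0-hour ratio could therefore adjust away early hyperoxia, which is part of what is being studied.

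**6. Cost of extra terms, on the plan's F test at n = 85 and R² = 0.15.**

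- Age (7 predictors): power 77.8%; 89 tested patients needed for 80%
- Age plus five site indicators (12 predictors): power 64.8%; 110 needed

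For the 1-df test of TWA-PaO2 at an assumed partial R² of 0.05, power is 96.9% at n = 280 and about 55% at n = 85, with either 6 or 12 predictors. Log downtime as a linear term uses the same single degree of freedom as the indicator.

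**The case against.** Several points on the other side stand, and they limit what can be claimed.

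- **Closure of the list.** A reader might infer that age and site are excluded from every model. The text fixes the set only for the cognitive models. For mRS it leaves room, though it names neither variable.
- **Self-contradiction.** A reader might say that the plan argues against categorising and then categorises. That argument concerns the exposure and the outcomes, not covariates, so there is no contradiction.
- **Earlier studies.** The team's previous model had hospital factors in sensitivity analyses, in 6326 patients from 120 hospitals, so it does not by itself show that six sites need a term in the main model. The A.3 account of the lost association does not say which adjustments removed it. It shows sensitivity to adjustment in general, not that age or site was responsible.
- **The PaO2/FiO2 flag.** It has a narrow stated purpose, to mark patients who cannot be oxygenated adequately, and a threshold suits that. A reader might infer that it is measured after the intervention starts. The plan does not say so; the defect is the missing time.
- **Charlson index.** An age-adjusted version would carry part of the age effect, but the plan does not specify one.
- **Size.** What matters is the correlation that remains after the named covariates, and that is unknown. At 0.1/0.1 the inflation is trivial.

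None of this supplies a reason to leave age and site unnamed or to keep downtime as yes/no.

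**Conclusion.** The point holds as an avoidable weakness in adjustment for a non-randomised exposure. Age and site are not named and downtime is coarsened, while the data for better adjustment are collected or known by design.

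The amount and direction of bias cannot be derived from the documents. The false-positive rates of about 5% to 52% are illustrations for a single omitted confounder under assumed correlations, with no other covariates in the model. They should not be read as the error rate of this study, and quoting only the upper part of the range would mislead. The 54–64% for downtime likewise rests on an assumed log-normal distribution. A corresponding figure for the PaO2/FiO2 cut depends too heavily on an assumed spread to be useful.

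The change is worth making because it needs only analysis-plan wording and no new data.

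**What to change.** In the mRS model and the cognitive models, including the repeats with TWA-SaO2:

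1. Prespecify age as a continuous covariate.
2. Prespecify site: fixed effects (five indicators) at n = 280, and a random intercept in the cognitive models of roughly 85 patients.
3. Enter downtime as log minutes in place of the 20-minute indicator.
4. Keep Charlson index (stating which version), rhythm and arrest location, and state that the list is final for both sets of models.
5. Keep PaO2/FiO2 <100 as a lung-injury marker, tied to a stated pre-intervention time point. Report the models with and without it, because that PaO2 also feeds TWA-PaO2. Do not replace it with a continuous 0-hour ratio in the main model.

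**Cost.** The change is to wording, plus a restated sample-size justification. On the plan's own steps, age alone takes 85 to 89 tested: 89 × 1.15 = 102.35, rounded up to 103, and 103/0.35 = 294.3, or 295 in total. Age plus fixed site effects would need 110 tested: 110 × 1.15 = 126.5, rounded up to 127, and 127/0.35 = 362.9, or 363 in total. The random intercept avoids spending five degrees of freedom in the small models, but a variance estimated from six sites is imprecise and may not remove all between-site confounding. Restating power for the 1-df test of TWA-PaO2 would match the question asked, and there the added terms cost almost nothing at a given partial R².
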